## 7 STATISTICAL METHODOLOGY AND STATISTICAL ANALYSES

As stated, the study is a single-arm study and will be purely descriptive and explorative. No formal hypotheses will be tested.

In general, this study will provide two types of outcomes

1. Outcomes on PFS, ToT and OS
2. Descriptive statistics on the population having palbociclib

### 7.1 DEFINITIONS

Incidence date	The date of the initial breast cancer diagnosis
Index date	The date of relapse or stage IV disease
Progression Free Survival (PFS)	The time from the date of relapse or stage IV disease (index date) to progression or death, whichever occurs first. Patients will be censored 31 December 2020. Progression of disease is based on scans and blood testing results.
Overall Survival (OS)	The time from index date to death of any cause.
Time on Treatment (ToT)	The date of palbociclib treatment start to date of treatment stop with palbociclib. ToT is estimated on the basis of variables RE203-RE205 and RE206-RE208 in the DBCG database
Visceral disease	Defined as metastases in the organs, i.e., liver, lung, ascites, pleural effusion, and metastases in the central nervous system. Visceral disease is based on the variable Location of metastases (RE10-18 + 80-81, 117-119, 219-222) in the DBCG database

PFIZER CONFIDENTIAL

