8.1. Definitions

PFS is defined as the date of relapse or stage IV disease (index date) to progression or death, whichever occurs first.

- Patients will be censored for PFS by 31 December 2020
- Progression of disease is based on scans and blood testing results

ToT is defined as date of palbociclib treatment start to date of treatment stop with palbociclib.

OS is defined as the date of relapse or stage IV disease (index date) until death of any cause

- Patients will be censored for OS by 01 May 2022
- Overall survival will also be reported after 6, 12 and 24 months (*landmark cut-off time points*)

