## 7.2 STATISTICAL ANALYSES

In the PFS, ToT and OS, Kaplan-Meier survival distribution functions will be estimated. Hence, if possible median PFS, ToT and OS as well as interquartile ranges (IQR) will be estimated. Unadjusted Kaplan Meier curves will be presented to illustrate time-to-event (PFS, ToT or OS).

For OS, OS-rates (%) at 6, 12 and 24-months (landmarks) will be estimated.

For the descriptive statistics, numbers and percentages will be provided and presented in tables, including cross tabulations (see section 8 for presentation of tables shells).

For

- 'all patients' vs. 'patients younger than 50 years'
- 'all patients' vs. 'patients aged 50-70 years'
- 'all patients' vs. 'patients older than 70 years'

statistical test (e.g.  $\chi^2$ -test) for differences in:

- 'types of metastases' (visceral, non-visceral or both)
- 'surgery' (yes or no)

will be performed.

All data analysis will be executed using statistical software such as SAS or Rstudio.

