	Adjuvant treatment*	Type 1: Median number of treatments of type 1: Type 2: Median number of treatments of type 2:

PFIZER CONFIDENTIAL

All included patients	Visceral metastases	Type of MBC	Primary MBC: N (%) Recurrent MBC: N (%)
		Number of metastases	0: N (%) 1: N (%) 2: N (%) >2: N (%)
		Location of metastases	Skin: N (%) Bone: N (%) Lung: N (%) Liver: N (%) CNS: N (%) Other: N (%)
		Surgery	Yes: N (%) No: N (%)
		Adjuvant treatment*	Type 1: Median number of treatments of type 1: Type 2: Median number of treatments of type 2:
Non-visceral metastases		Type of MBC	Primary MBC: N (%) Recurrent MBC: N (%)
		Number of metastases	0: N (%) 1: N (%) 2: N (%) >2: N (%)
		Location of metastases	Skin: N (%) Bone: N (%) Lung: N (%) Liver: N (%) CNS: N (%) Other: N (%)
		Surgery	Yes: N (%) No: N (%)
		Adjuvant treatment*	Type 1: Median number of treatments of type 1: Type 2: Median number of treatments of type 2:
		Time from initial breast cancer diagnosis (incidence date) to relapse	Median time

\* The result may be more than 2 types of adjuvant treatment.

PFIZER CONFIDENTIAL

**Table 4.** Progression Free Survival (PFS)\*

Endpoint	Population	Subgroup	Outcome	Result
Primary	Included patients treated with palbociclib in combination with AI	-	PFS	Median and IQR
Primary	Included patients treated with palbociclib in combination with AI	Patients younger than 50 years	PFS	Median and IQR
		Patients aged 50-70 years	PFS	Median and IQR
		Patients older than 70 years	PFS	Median and IQR
Primary	Included patients treated with palbociclib in combination with AI	Patients with visceral disease	PFS	Median and IQR
		Patients without visceral disease	PFS	Median and IQR
Secondary	Included patients treated with palbociclib in combination with Fulvestrant	-	PFS	Median and IQR
Secondary	Included patients treated with palbociclib in combination with Fulvestrant	Patients younger than 50 years	PFS	Median and IQR
		Patients aged 50-70 years	PFS	Median and IQR
		Patients older than 70 years	PFS	Median and IQR
Secondary	Included patients treated with palbociclib in combination with Fulvestrant	Patients with visceral disease	PFS	Median and IQR
		Patients without visceral disease	PFS	Median and IQR

Table note: \* Following definition of PFS in section 7.1.

**Table 5.** Time on Treatment (ToT)\*

Endpoint	Population	Subgroup	Outcome	Result
Primary	Included patients treated with palbociclib in combination with AI	-	ToT	Median and IQR

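### PFS and OS are timed from relapse or stage IV disease although patients enter only by starting palbociclib later, so OS is conditioned on survival to that start, 2nd-line PFS is not PFS on palbociclib, and the 6/12/24-month OS has no single origin

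*SAP*

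**What the plan says.** **Time origin.** SAP 7.1 measures PFS as "The time from the date of relapse or stage IV disease (index date) to progression or death, whichever occurs first" and OS as "The time from index date to death of any cause". Protocol 8.1 agrees: "PFS is defined as the date of relapse or stage IV disease (index date) to progression or death, whichever occurs first", and "OS is defined as the date of relapse or stage IV disease (index date) until death of any cause". The note under SAP Table 4 ties the PFS output to this wording ("Following definition of PFS in section 7.1"), and the note under Table 6 does the same for OS. ToT, the other primary endpoint, has a different origin: "The date of palbociclib treatment start to date of treatment stop with palbociclib".

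**Entry.** Protocol 9.2.1 and SAP 4 admit patients who began palbociclib as 1st or 2nd line between 01 January 2017 and 31 December 2020. No criterion limits how long before that the relapse may lie. Criterion 4 names an inclusion date that may be the progression that led to palbociclib. No endpoint is measured from that date.

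**Analysis.** SAP 7.2 plans unadjusted Kaplan-Meier curves. Neither document mentions delayed entry or left truncation.

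**OS at fixed times.** SAP 7.2 states: "For OS, OS-rates (%) at 6, 12 and 24-months (landmarks) will be estimated". Protocol 9.7 counts the 6, 12 and 24 months from treatment initiation, and the Protocol's abstract, section 8 and Table 1 refer to months on palbociclib. Protocol 8.1 lists the same times under index-date OS with no origin of their own.

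**The concern.** A patient who dies between relapse and palbociclib start can never be in the cohort. If the clock starts at relapse, the interval up to palbociclib carries no deaths by construction, and a Kaplan-Meier estimate without delayed entry counts it as survival.

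For PFS the difficulty is what is being measured. A 2nd-line patient may already have progressed once after relapse, and criterion 4 itself refers to such a progression. The definition does not say which progression is the event, so two analysts could follow it and report different quantities.

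The affected results are PFS with AI (a primary endpoint), PFS with fulvestrant and both OS endpoints. The two primary endpoints would not share a time zero, so PFS and ToT in the same patients could not be read against each other directly. SAP Tables 4-6 are not split by line, so a reader could not separate the affected patients.

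**Working it through.** **1. The plan's own time figure.** Protocol 9.7 gives the maximum OS follow-up, counted from a first treated patient on 01 January 2017, as close to 5.5 years. From that date to 01 May 2022 is 1,946 days; 1,946 / 365.25 = 5.33 years. The rounding is loose but harmless. The figure is a maximum only if OS starts at treatment, because a relapse may be earlier. Section 9.7 therefore counts from treatment while 8.1 counts from relapse. The documents contain no other derived figure to reproduce.

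**2. The two readings of PFS for a 2nd-line patient.** Let the sequence be relapse, earlier line, progression, palbociclib, second progression.
- Read literally, the event is the first progression after the index date. It precedes palbociclib, so the result is the earlier regimen's PFS.
- If only progression after palbociclib start counts, the result is the earlier line's time plus time on palbociclib.

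**3. Inputs for an illustration.** The documents give neither the line split nor the gap, so these are stand-ins.
- Earlier-line median m1: 10.2 to 14.5 months, from the first-line letrozole-alone medians in Protocol 7.
- PFS from palbociclib start: 20.0 months in 1st line (the real-world figure in Protocol 7) and 9.5 months in 2nd line (a palbociclib-fulvestrant figure in Protocol 7, borrowed here for AI).
- OS median from palbociclib start: 30 months, the middle of the 2-3 years in Protocol 7. That passage states no origin.
- 2nd-line share p: 10% or 30%. Times are exponential, and survival after palbociclib start is the same in both lines and independent of the earlier line's length.

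**4. Formulas.** For a single time with median m, S(t) = 2^(-t/m). For an earlier time plus a later time, with a = ln2/m1 and b = ln2/m2, S(t) = [b·exp(-at) - a·exp(-bt)] / (b - a). The cohort curve is (1 - p)·S(1st line) + p·S(2nd line).

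**5. Median PFS, AI cohort.** From palbociclib start with p = 30%, solve 0.7·2^(-t/20) + 0.3·2^(-t/9.5) = 0.5, which gives t = 15.8. The other cells follow by replacing the 2nd-line term.

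| 2nd-line share | From palbociclib start | Earlier line added | First progression counts |
|---|---|---|---|
| 10% | 18.5 | 20.5-21.0 | 18.6-19.3 |
| 30% | 15.8 | 21.4-22.9 | 16.2-18.1 |

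**6. 24-month OS.** From palbociclib start: 2^(-24/30) = 57.4%. For 2nd line with m1 = 14.5, a = 0.0478 and b = 0.0231, so S(24) = (0.0231×0.3175 - 0.0478×0.5743) / (0.0231 - 0.0478) = 81.5%; with m1 = 10.2 it is 76.9%. With p = 30%: 0.7×57.4 + 0.3×76.9 = 63.3% and 0.7×57.4 + 0.3×81.5 = 64.6%. With p = 10%: 59.4% and 59.8%. With OS medians of 24 and 36 months, the start-based 50% and 63% become 52-53% and 65% at p = 10%, and 57-58% and 68-69% at p = 30%.

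**7. 1st line only.** A fixed gap g adds g to the PFS and OS medians. With a 30-month OS median, 24-month OS becomes 2^(-(24 - g)/30): 58.1% at g = 0.5 month and 61.6% at g = 3 months.

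**8. Delayed entry.** A simulation drew 400,000 patients with a 30-month median OS and admitted only those alive at palbociclib start. The included cohort had 40% in 2nd line, the 2nd-line delay had a median of 14.5 months, and the 1st-line delay was 1 month. The plan's estimator gave 65.7% at 24 months. Delayed entry gave 57.3%, as did timing from palbociclib start.

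**The case against.** The study is single-arm and tests no hypothesis, so no treatment comparison is distorted. That stands. OS from relapse is also a legitimate quantity, so part of the difference from start-based OS is a different estimand and not bias. That stands too, but the legitimate version needs delayed entry, which is not planned.

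If AI patients are mostly 1st line, primary PFS shifts by little more than the relapse-to-start gap. This is possible; the documents do not say, and they do not equate AI with 1st line.

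It can be argued that the literal PFS reading is strained, because Table 1 lists palbociclib dates and no progression date from before palbociclib. But a definition that stops at the earliest progression after the index date selects exactly the progression that criterion 4 describes. Treating criterion 4's date as time zero would remove most of the 2nd-line problem, but SAP 7.1 defines another date and the tables cite 7.1.

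Three stronger inferences are not supported:
- A reader might conclude that the results could not be set beside the cited trial and real-world medians. The documents do not give the time origins of those figures.
- A reader might use the 4.6-month control-arm median as the earlier line and infer that PFS could be understated. Protocol 7 describes that trial as 2nd line and beyond, so it is a poor stand-in for a first line. With 10.2-14.5 months, no downward shift appears in the cohorts above.
- A reader might see the 6/12/24-month conflict as purely Protocol against SAP. Protocol 8.1 and 9.7 also disagree with each other.

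**Conclusion.** The point holds on the text. As written, OS credits patients with an interval they had to survive in order to be included. PFS for 2nd-line patients is either the earlier regimen's result or the sum of two lines. A small numerical change under the first-progression reading does not rescue it, because the number would still describe another treatment. The origin of the 6/12/24-month OS is unsettled within the Protocol and between the Protocol and the SAP.

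The definitional fault is certain; its size is not known. Under the stated assumptions, median PFS with AI moves by roughly 0.1 to 2.5 months with 10% in 2nd line and by 0.4 to 7.1 months with 30%, depending on the reading. With a 30-month OS median, 24-month OS rises by about 2 points with 10% and 6 to 7 points with 30%. For 1st-line patients the shift is only the gap between relapse and palbociclib start. These figures show direction and possible scale; they are not estimates for this cohort. Because a primary endpoint's definition is affected, the point should be settled before the analysis is run.

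**What to change.** In Protocol 8.1 and SAP 7.1, declare one time zero for PFS, OS and the 6/12/24-month OS: palbociclib start (RE203-RE205). This date already anchors ToT and agrees with Protocol 9.7. Count only progression or death after it.

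Any OS curve from relapse should be secondary and use delayed entry at palbociclib start. It should state the assumption that time to palbociclib is independent of later survival. Delayed entry cannot correct a gap that every patient shares. It should not be used for PFS, because a 2nd-line patient's first progression can precede entry.

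Reconcile criterion 4 (Protocol 9.2.1 and SAP 4), Protocol 8.1, 9.7 and Table 1, and SAP 7.1, 7.2 and Table 6.

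Cost: revised SAP wording, and the protocol amendment that section 9.7 foresees when a primary endpoint definition changes. The start date is already among the listed variables. Dated progressions are not listed in Table 1 of either document; PFS needs them under any origin, so their availability must be confirmed. OS will be reported as shorter, and PFS as shorter than under the later-progression reading.

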Descriptive statistics, including stratification on sub-groups. In the PFS and OS analyses, Kaplan-Meier survival distribution functions will be estimated. Besides an OS analysis with censoring at 01 May 2022, supplementary OS analyses will be made after 6, 12 and 24 months of palbociclib treatment (landmark cut-off time points). A separate Statistical Analysis Plan (SAP), including shell tables, will be developed prior to data analysis.

Milestones

Final Protocol: 17 December 2021

Final Statistical Analysis Plan: 31 January 2022

Start of data collection (first subject first visit [FSFV] – database study, historic data): 01 February 2022

Data setup: 01 February 2022

Data analyses: 01 February-01 August 2022

End of data collection (last subject last visit [LSLV] – database study, historic data): 01 August 2022

[figure not shown]
DBCG Final study report: 30 September 2022

Manuscript ready for submission: 15 December 2022

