9. RESEARCH METHODS

9.1. Study design

The study is designed as a secondary data collection NIS based on retrospective data from an existing registry focusing on HR+/HER2- locally advanced or metastatic breast cancer treated with palbociclib. The study is a single-arm study only focusing on patients treated with palbociclib in Denmark.

The study is purely descriptive and explorative. No formal hypotheses will be tested in the study.

Since the establishment in 1976, the DBCG has maintained a clinical registry for early breast cancer patients in Denmark in which surgeons, pathologists, medical geneticists and oncologists report data regarding diagnosis, treatment and follow-up of breast cancer. This is a unique clinical registry. This well-established breast cancer registry (1976) managed by DBCG was expanded in 2017 to include retrospective and prospective clinical and pathological data on breast cancer patients with a relapse. This includes both the primary MBC (De Novo) and recurrent MBC.

The DBCG registry focusing on relapses which the study will be based is one of several DBCG registries. It is estimated that end of 2021 the DBCG registry will include all Danish patients with locally advanced or metastatic breast cancer. The data and records in the registry are based on systematic review following a standard case report form of all electronic patient records of patients diagnosed with locally advanced or metastatic breast cancer.

The data collection and the ongoing populating of the DBCG registry are performed by healthcare professionals in the DBCG secretariat and are conducted independently of this study. Compared to other exhaustive national Danish patient registries, the DBCG registry contains detailed clinical and pathological data about the treatment patterns of patients with

HR+/HER2- locally advanced or metastatic breast cancer. Thus, the registry is an important and well-suited source to address the research questions (See section 8).

The present NI-Study will only use and rely on the existing data in the DBCG registry and no additional data will be collected as part of the study, as well as no review of medical records will be made. Therefore, the present NI-Study is defined as a retrospective secondary data collection study, where all data needed for the analysis exist as structured data by the time of study start. This also means that there are no human review of unstructured data conducted as part of the protocol.

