9.2. Setting

In the DBCG registry, patients with HR+/HER2- locally advanced or metastatic breast cancer treated with palbociclib will be identified. Palbociclib was approved by the European Commission (EC) and European Medicines Agency (EMA) in November 2016. Hence, the study period will be 2017-2020. A follow-up on patients until 01 May 2022 in terms of the estimation of OS will be made.

The CDK4/CDK6 inhibitors ribociclib and abemaciclib were approved later (2018 and 2020, respectively) and data regarding these treatments are currently not included in the registry. The study will only include patients treated with palbociclib.

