9.7. Data analysis

In general, some research questions will be addressed via descriptive statistics, including stratification on sub-groups. In the PFS and OS analyses, Kaplan-Meier survival distribution functions will be estimated, implying that statistics on median survival expectedly will be available. Overall survival will be estimated for all patients with a censoring of data by 01 May 2022, ie, why the maximum follow-up period for the first treated palbociclib patient 01 January 2017 will be close to 5.5 years. In Kaplan-Meier landmark analyses OS will furthermore be analysed and reported after 6, 12 and 24 months from treatment initiation.

A separate SAP, including shell tables, will be developed prior to data analysis. The SAP will be dated, filed, and maintained by the sponsor. The SAP will also include precise definitions of the sub-groups. The SAP may modify the plans outlined in the protocol; any major modifications of primary endpoint definitions or their analyses would be reflected in a protocol amendment.

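### PFS follow-up stops on the last permitted palbociclib start day, 16 months before the OS cut-off and without a stated reason; a later common cut-off, if progression is registered that far, is a cheap improvement

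*SAP*

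**What the plan says.** PFS in patients receiving palbociclib with an AI is a primary endpoint (SAP 5). SAP 7.1 measures it from relapse or stage IV disease (the index date) to progression or death and adds: "Patients will be censored 31 December 2020". Protocol 8.1 agrees: "Patients will be censored for PFS by 31 December 2020".

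For OS, Protocol 8.1 uses a later date: "Patients will be censored for OS by 01 May 2022". Protocol 9.2 sets the study period as 2017–2020 and extends follow-up for OS alone: "A follow-up on patients until 01 May 2022 in terms of the estimation of OS will be made".

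The inclusion criteria in both documents allow palbociclib to start from 01 January 2017 to 31 December 2020. SAP 7.2 plans Kaplan-Meier medians and interquartile ranges where they can be estimated, and SAP Table 4 has a cell for both in the AI cohort, overall and in five subgroups.

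**The concern.** The closing date for treatment start also serves as the closing date for progression. A patient who starts on 31 December 2020 has no on-treatment PFS follow-up, and no patient has more than 48 months of it. Deaths are nevertheless followed for a further 16 months. Protocol 9.2 explains the 2017–2020 window, but neither document says why progression stops at its end, or to what date progression is registered.

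If progression after 2020 is in the register, the plan sets aside events on a primary endpoint that it could use. That would cost precision of the AI median and, at the longer cited medians, the upper quartile that Table 4 is meant to show.

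**Working it through.** The documents contain no event or precision calculation for PFS, so there is no plan figure to reproduce.

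**Dates.** 31 December 2020 to 01 May 2022 is 486 days; 486 / 30.4375 = 16.0 months. To 31 December 2021 it is 12.0 months. The start window is 48 months.

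**Inputs from Protocol 7.** Cited median PFS with palbociclib plus letrozole: 20.0 months (US real-world study), 24.8 months (phase 3) and 27.6 months (phase 3, extended follow-up). With palbociclib plus fulvestrant: 9.5 months.

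**Assumptions not in the documents.** Starts uniform over 48 months; exponential PFS from palbociclib start; 1,000 AI patients (Protocol 9.5 gives only 1,500 in total, without a split); 31 December 2021 as an intermediate cut-off. 01 May 2022 is a best case for progression, because Protocol 9.1 says that "all data needed for the analysis exist as structured data by the time of study start" and data collection starts on 01 February 2022.

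**Share with a PFS event.** With L = ln 2 / median and a = months of follow-up added after 31 December 2020:

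share = 1 − [exp(−L·a) − exp(−L·(48 + a))] / (48·L)

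Example, median 24.8: L = 0.02795 and 48·L = 1.3416.
- a = 0: 1 − (1 − 0.2614)/1.3416 = 0.449
- a = 12: 1 − 0.7151 × 0.5505 = 0.606
- a = 16: 1 − 0.6394 × 0.5505 = 0.648

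| Median (months) | 31 Dec 2020 | 31 Dec 2021 | 01 May 2022 |
|---|---|---|---|
| 20.0 | 51% | 68% | 72% |
| 24.8 | 45% | 61% | 65% |
| 27.6 | 42% | 57% | 61% |

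Per 1,000 AI patients this is about 150–165 more events at the end of 2021 and about 190–210 more at 01 May 2022.

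**Precision of the median** (simulation, n = 1,000, index date equal to palbociclib start). At a median of 24.8 months the SD is about 1.4 months now, 1.2 at 31 December 2021 and 1.1–1.2 at 01 May 2022. The median was reached in every run at every date.

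**Upper quartile.** Under an exponential curve it lies at twice the median: 40.0, 49.6 and 55.2 months. The last two are beyond 48 months but within 60 and 64. Share of runs in which the curve reaches 25%, for medians 20.0/24.8/27.6:

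| Mean lead, index to palbociclib | 31 Dec 2020 | 31 Dec 2021 | 01 May 2022 |
|---|---|---|---|
| 0 months | 97/33/10% | 100/99/80% | 100/100/96% |
| 6 months | 100/90/74% | 100/100/98% | 100/100/100% |

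With a mean lead of 12 months it is reached in at least 98% of runs at every date. Reaching it can still mean little: with a 6-month lead at the present date, the median number at risk there is 41/12/7 of 1,000.

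**Bias.** A fixed calendar cut-off leaves Kaplan-Meier unbiased if index and palbociclib start coincide. If index is earlier, event time = lead + on-treatment PFS and censoring time = lead + time from start to cut-off. The two share the lead and are no longer independent. With an exponential lead of mean 12 months and an on-treatment median of 24.8, the true median from index is 37.9 months. The mean Kaplan-Meier median is about 40.0 at the present cut-off and 38.3 at 01 May 2022.

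**Fulvestrant.** At 9.5 months and an assumed 300 patients, the upper quartile is always reached and the SD of the median is 0.85 now against 0.78–0.79 later.

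**The case against.** The strongest reply is that nothing is wrong: both documents give the same date, Protocol 9.2 frames 2017–2020 as the study period and limits the extension to OS, and the study tests no hypothesis. That stands. A reader might infer a drafting slip or a contradiction, and the documents do not support it; the date looks deliberate. Only the reason is missing.

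Second, the gain depends on data nobody outside the register can see. This also stands. Protocol 9.1 says: "It is estimated that end of 2021 the DBCG registry will include all Danish patients with locally advanced or metastatic breast cancer". One might read that as progression being complete through 2021, but it concerns which patients are in the register, not how far their progression is followed. So it cannot be said that usable events are being discarded, only that they may be.

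Third, the affected output is narrow. The AI median is reached regardless, fulvestrant hardly changes, and the interquartile range is promised only where estimable. At 20.0 months, the only real-world AI median cited, the upper quartile is already reached in about 97% of runs. The poor figures need the trial medians and a short lead, and the documents do not settle the lead: PFS runs from relapse or stage IV disease and second-line patients are eligible. All of this limits the size of the point. It gives no reason to leave out follow-up that may be available for a primary endpoint.

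Fourth, a later PFS date does nothing for ToT, the other primary endpoint, whose definition has no censoring date in either document. True, but a separate question.

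**Conclusion.** A worthwhile, inexpensive improvement, not a defect that invalidates the analysis. If progression is completely registered beyond 2020, a later cut-off would add about 150–210 PFS events per 1,000 AI patients and modestly tighten the AI median. It would also make the upper quartile attainable, or better supported, if the true median is near 25 months or more. These sizes rest on uniform starts, exponential PFS, the cited medians and an assumed 1,000 AI patients; 01 May 2022 is the optimistic end.

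Two stronger conclusions are not supported. The primary result is not at risk of being inestimable, since the AI median is reached at either date. Nor would a later date make the Kaplan-Meier estimate unbiased. Where index precedes palbociclib start, the upward bias shrinks (about 2.1 months to 0.4 in the 12-month-lead example) but does not vanish.

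**What to change.** Before any outcome analysis, have the register's analysts establish the date to which progression is completely registered.

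- If that date is after 31 December 2020, write it, no later than 01 May 2022, into SAP 7.1 and Protocol 8.1 as the single PFS cut-off for progression and death together. Do not count later deaths without equally complete progression: SAP Table 1 names a second source for death dates, so deaths could be more current than progression. Keep 31 December 2020 as the last start date for inclusion and as a sensitivity cut-off.
- If progression is complete only to 31 December 2020, keep the date and state that reason.
- In either case, add the numbers of events and censored patients to Table 4.

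The cost is one completeness check, a sentence in each document and, if the date moves, a protocol amendment, since Protocol 9.7 says that "any major modifications of primary endpoint definitions or their analyses would be reflected in a protocol amendment". If the date stays, the cost is the check, one explanatory sentence and the added counts.

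### PFS is censored at one calendar date with no rule for patients whose progression status was abstracted only to an earlier date, so PFS may be overstated unless every record reaches the cut-off

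*SAP*

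**What the plan says.** SAP section 7.1 defines PFS as "The time from the date of relapse or stage IV disease (index date) to progression or death, whichever occurs first" and adds "Patients will be censored 31 December 2020". Protocol section 8.1 has nearly the same rule, "Patients will be censored for PFS by 31 December 2020", and adds "Progression of disease is based on scans and blood testing results". PFS in the aromatase-inhibitor cohort is a primary endpoint, and the fulvestrant cohort is secondary. Both are estimated by Kaplan-Meier with median and IQR (SAP 7.2).

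On where progression data come from, Protocol section 9.1 says "The data and records in the registry are based on systematic review following a standard case report form of all electronic patient records". It describes filling the register as ongoing and independent of this study, and says "no additional data will be collected as part of the study, as well as no review of medical records will be made".

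Neither variable list (Protocol 9.3, SAP 5.1) contains a date of last record review, last contact or last assessment. SAP section 6 limits the study to patients whose registration is complete and concludes that missing data need no handling. It does not define complete, and does not link it to follow-up through the PFS cut-off.

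**The concern.** Censoring everyone at a calendar date is correct when everyone was observed to that date. Here progression is observed only up to the last assessment that registry staff abstracted. If that point falls before 31 December 2020, the patient cannot show a progression afterwards but stays in the risk set as progression-free until the cut-off. With no last-review date in the extract, the analyst cannot separate patients who had not progressed from patients whose record had not yet been updated.

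For any such patient the error goes one way: a missed progression lengthens estimated PFS. The study has one arm, so no comparator shares the error. The protocol intends its results to supplement the randomised trials and published real-world studies, for which it quotes medians of 24.8, 27.6 and 20.0 months. A reader will set the Danish median beside those figures.

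**Working it through.** The documents state no PFS bias or event figure, so there is nothing to reproduce. The check asks how far the median would move if some records ended early.

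**Inputs from the documents.** Treatment starts from 1 January 2017 to 31 December 2020, a 48-month window. Cut-off 31 December 2020. Kaplan-Meier median. Illustrative true medians: 20.0 months (real-world palbociclib plus letrozole, Protocol 7), 27.6 months (phase 3 extended follow-up, Protocol 7) and 9.5 months (palbociclib plus fulvestrant, Protocol 7).

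**Assumptions not in the documents.** Exponential PFS; index dates uniform over 48 months; 10% of PFS events are deaths; median 24 months from progression to death; a share *f* of records ending *L* months before the cut-off, unrelated to prognosis. Deaths are treated as captured to the cut-off even where progression is not, because the death date is a separate variable.

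**Hand check.** At time *t* after index, with uniform entry, the fraction of the risk set still under abstraction is about 1 − *fL*/(48 − *t*). The Kaplan-Meier median then solves

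*t* − *fL* · ln[48/(48 − *t*)] = true median.

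For *f* = 25%, *L* = 12 and a true median of 20.0, *fL* = 3. At *t* = 21.8, ln(48/26.2) = 0.606 and 21.8 − 3 × 0.606 = 19.98, so the estimate is about 21.8. The formula ignores unrecorded progressors accumulating in the risk set (which pushes the estimate up) and captured deaths (which pull it down). Simulation gives 22.3 without captured deaths and 21.5 with them, on either side of the hand value.

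**Simulation, fixed lag, deaths captured** (400,000 patients per scenario; estimated median for *L* = 3 / 6 / 12 months):

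| True median | *f* = 10% | *f* = 25% | *f* = 50% |
|---|---|---|---|
| 9.5 | 9.6 / 9.7 / 9.8 | 9.7 / 9.8 / 10.2 | 9.8 / 10.2 / 11.1 |
| 20.0 | 20.2 / 20.3 / 20.5 | 20.4 / 20.8 / 21.5 | 20.7 / 21.6 / 23.6 |
| 27.6 | 27.8 / 28.1 / 28.6 | 28.3 / 28.7 / 30.1 | 28.9 / 30.3 / 34.0 |

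With *f* = 0 the medians are 9.5, 19.9 and 27.5, that is, no bias beyond simulation error.

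**Simulation, spread lag, deaths captured.** A share of 10–30% has last review uniform over the 12 or 24 months before the cut-off (mean 6 or 12). A true 20.0 reads about 20.4–22.1 and a true 27.6 about 28.1–30.7. Repeat runs move these by 0.1 to 0.2. Relative size: 20.4/20.0 = 1.02 and 22.1/20.0 = 1.105; 28.1/27.6 = 1.02 and 30.7/27.6 = 1.11.

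**Ending follow-up at last review for everyone**, with no event of either kind counted after it, returns 9.4–9.5, 19.9–20.0 and 27.5–27.7 across the fixed-lag scenarios.

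**The case against.** The strongest reply is that no passage says any record ended before 31 December 2020, and several lean the other way. The abstract gives "Start of data collection (first subject first visit [FSFV] – database study, historic data): 01 February 2022", 397 days or 13.0 months after the cut-off. Protocol 9.1 adds "It is estimated that end of 2021 the DBCG registry will include all Danish patients with locally advanced or metastatic breast cancer" and says all data needed for the analysis will exist in structured form at study start. SAP 6 admits only complete registrations. This makes long gaps less likely, and it stands as a limit on the point. It does not settle the matter: the coverage statement is an estimate of which patients are in the register, not of how far each is followed, and completeness is undefined.

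A reader might infer that the SAP tightened the protocol by dropping the word *by*, which could allow earlier censoring. The documents do not support that. Protocol 9.7 says major changes to primary endpoint definitions would lead to an amendment, and none is recorded, so the SAP most naturally restates the protocol rule. Either way, neither document supplies a rule for records that stop early.

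Two further objections stand in part. Ignoring captured deaths would inflate the illustration: the top of the range for a true 27.6 would be 32.3 months (17%) instead of about 30.7 (11%). The study is also purely descriptive, with no test at risk. But a descriptive single-arm study delivers its median as the result.

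**Conclusion.** The point holds conditionally. The plan sets one calendar censoring date, gives no rule for progression status known only to an earlier date, and lists no variable that would reveal such patients. PFS may therefore be overstated unless every record was reviewed through 31 December 2020.

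It would go too far to say that PFS is biased upward. That requires records ending before the cut-off, which the documents neither report nor rule out.

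The size depends wholly on the assumed share and lag. With deaths captured and 10–30% of records ending on average 6–12 months early, the median is about 2–11% too long. With complete abstraction it is zero. These figures also rest on exponential PFS, uniform entry, the assumed death pattern, and review timing unrelated to prognosis.

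**What to change.** Change the PFS entry in SAP 7.1 to say: *PFS follow-up for each patient ends at the earlier of 31 December 2020 and the last date through which that patient's progression status was abstracted in the DBCG register; progression and death count as PFS events only up to that date.* Add that date to SAP Table 1, report how many patients are censored before the cut-off, and give the fixed-date analysis, with all deaths to the cut-off counted, as a sensitivity analysis.

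The limit on deaths matters. If only event-free patients were censored at last review while later deaths still counted, survivors would leave the risk set and deaths would not. The median would then be slightly too short (27.6 becomes about 27.0 at the top of the assumed range). The date should also be defined as one thing, abstraction of progression status, because last contact can be a different date.

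The cost is slightly less person-time and one extra registry date in the extract. Whether the register holds that date is not stated. If it does not, the report should say that PFS assumes complete progression abstraction to 31 December 2020 and may be overstated. If all records do reach the cut-off, the new rule changes no result.
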